**B. Children**

N/A

**C. Pregnant Women and Fetuses**

N/A

**D. Neonates of Uncertain Viability or Nonviable Neonates**

N/A

**E. Nonviable Neonates**

N/A

**F. Biomedical and Behavioral Research Involving Prisoners**

N/A

---

**45. Medical Devices (Checklist)**

*Complete this checklist if the research evaluates the safety or effectiveness of a medical device. If more than one medical device is being evaluated, provide the requested information for each.*

A. Device Name: Mecta Spectrum 5000Q paired with Soterix Medical 4X1 HD-ECT Multi-Channel Stimulation Interface

B. Manufacturer: Soterix Medical  
[name]  
[name]  
[name]  
Contact: [name]  
Email: [[contact]](mailto:[contact])

C. Does the research involve a Significant Risk Device under an IDE?

Yes. Include documentation of the FDA approval of the IDE with your submission. *Acceptable methods of documentation include: (1) FDA letter noting IDE number and approval status; (2) Industry sponsor letter noting IDE number and FDA approval status; or (3) FDA-approved industry sponsor protocol with IDE number noted*

No

D. Is the research IDE-exempt?

Yes. Include a FDA letter with your submission noting the determination that the research is IDE-exempt or a letter from the sponsor (or sponsor-investigator) justifying why they believe the research is IDE-exempt\*.

No

E. Does the research involve a Non-Significant Risk (NSR) Device?

Yes. Include a FDA letter with your submission noting the determination that the research is NSR or a letter from the sponsor (or sponsor-investigator) justifying why they believe the research is NSR\*\*.

No

\* This FDA guidance includes a description for when a device study is exempt from the IDE requirements:

<http://www.fda.gov/downloads/RegulatoryInformation/Guidances/UCM127067.pdf>

\*\*This FDA guidance includes information on how to differentiate between Significant Risk and Non-Significant Risk device studies:

<http://www.fda.gov/downloads/RegulatoryInformation/Guidances/UCM126418.pdf>

## 46. Export Control (Checklist)

N/A

## 47. Data Transfer/Sharing (Checklist)

Complete this checklist if the research involves transferring/sharing of data with an external entity (institution, company, etc.).

A. Will data be transferred/shared with an external entity (institution, company, etc.)?

Yes

No. **The remainder of this section does not apply.**

B. Indicate if the data is incoming and/or outgoing: Outgoing

C. Provide the name of the entity that data will be transferred/shared with: De-identified clinical and imaging data will be uploaded to the National Institute of Health National Data Archive at 6-month intervals. This is an NIH requirement.

D. Provide the contact name, email and phone number with whom data is being transferred or shared with: <https://nda.nih.gov>

E. Who is responsible for transmission of the data? Study PI ([name]) and team

F. Who is responsible for receiving the data? NIMH Data Archive

G. Describe how the data will be transferred/shared. Please note data cannot be transferred/shared without assistance from UNM HSC IT. **Requesting HSC Central IT Transfer is detailed on the Sponsored Projects website:** De-identified data will be uploaded to NIMH Data Archive through the COINS (<https://coins.trendscenter.org>) system.

H. For data being transferred/shared with outside locations or entities, describe the following:

- Where is data storage and how will it be maintained in a secure manner (i.e. encryption, password protection, use of Qualtrics or REDCap, etc)? <https://coins.trendscenter.org>. Data is encrypted and password protected.
- What is method in which data will be collected and stored (i.e. electronic, hard copy, etc)? Data will be initially recorded in paper charts and then electronically uploaded to COINS site. The data will be then be uploaded at 6-month intervals from COINS to the NIMH Data Archive.
- How long will the data be stored? *Paper charts will be kept for the duration of the study. COINS and NIMH Data Archive (de-identified data) will be kept indefinitely.*
- Who will have access to data? *Study team will have access to the COINS data; Other investigators must access NIMH Data Archive through established protocols (<https://nda.nih.gov/get/access-data.html>).*

I. Please list all specific data elements, variables, etc. to be sent out and/or received. Indicate if the data contain identifiers and health information. Please note that identifiers that MUST be removed to make health information de-identified are as follows: Names, All geographic subdivision smaller than a State, All elements of year (except year), Telephone, Fax numbers, E-mail addresses, Social Security, Medical record number, Health plan beneficiary, Account numbers, Certificate/license numbers, Vehicle identifiers and serial numbers, Device identifiers and serial numbers, Web URLs, IP address numbers, Biometric identifiers, full face photographic images, and Any other unique identifying number, characteristic or code.) All identifying elements outlined above will not be included in COINS or uploaded to the NIMH Data Archive. All subjects participating in this protocol have provided permission for the transfer of their de-identified data to the NIMH Data Archive.

J. If the research requires the access, use, or disclosure of any of the 18 individually identifiable protected health information (PHI) identifiers that can be used to identify,

contact, or locate a person (e.g., name, medical record number, etc.), are the subjects going to consent to or authorize the disclosure of their individually identifiable health information? Not applicable.

- a. **Or** is HIPAA authorization altered or waived? Not applicable
- K. What is the classification of the data: de-identified, limited data set, protected health information, or other type? De-identified.
- L. Does the request to transfer/share data include clinical data that belongs to the UNM Health Systems? The included information will be generated for research purposes only (including imaging data acquired at Mind Research) and does not belong to UNM.
- M. Does the data to be transferred/shared include information about patients seen at external health system or at a third party medical provider? Not applicable.
- N. Is the external entity a “covered entity”? Not applicable.
- O. Is the data that is going to be transferred/shared owned or partially owned by another party or have any type of restrictions including regulatory restrictions (i.e. HIPAA, FERPA, etc.)? De-identified data transferred to the NIMH Data Archive (NDA) will be coded using a unique code known as a Global Unique Identifier (GUID). Use of the GUID minimizes risks to study participants because it keeps one individual’s information separate from that of another person without using names, addresses, or other identifying information. The unique code also allows the NDA to link together all submitted information on a single participant, giving researchers access to information that may have been collected elsewhere. The GUID is a computer-generated alphanumeric code [example: NDA-1A462BS] that is unique to each research participant (i.e., each person’s information in the NDA—or each subject’s record—has a different GUID). The process of assigning a GUID prevents direct identifiers from ever being transmitted or stored in the NDA. We will ensure that no direct identifiers are transmitted in this process.
- P. Is the data publicly available? If yes, please provide details: As per the NIMH Data Archive site, “Summary information on the data shared in NDA is available in the NDA Query Tool without the need for an NDA user account. To request access to record-level human subject data, you must submit a Data Access Request.
- Q. Does the data include information about substance abuse treatment, sexually transmitted diseases, genetic testing results, HIV/AIDS testing results, and/or mental health? Mental health data will be included with this data.

## **48.Specimen Transfer/Sharing (Checklist)**

N/A

PROTOCOL TITLE: Electroconvulsive therapy amplitude titration for improved clinical outcomes in late-life depression

NCT number: NCT04621786

Date of document: 11/19/2020

1. Data Analysis

Preliminary Data: Amplitude titration has been completed with non-human primates but has yet to be completed with human subjects and modern ECT parameters. I/E_{brain} bridges the gap from amplitude titration in non-human primates to changes in hippocampal neuroplasticity in human subjects. I/E_{brain} is the ratio of electrode current strength (I) to the E-field strength in the brain (E_{brain})²¹. E_{brain} will be computed as the 90th percentile of E-field magnitudes from all voxels in the brain, serving as an estimate of the peak induced field strength while avoiding the influence of tissue boundary effects that could bias the absolute maximum E-field values. For example, one subject with 800 mA extracranial amplitude produces 0.8 V/cm 90th percentile E-field strength. The ratio would be 1000 mA/V/cm, which means 1000 mA produces 1 V/cm. A second subject with the same 800 mA extracranial amplitude produces 1.2 V/cm 90th percentile E-field. The ratio would be 667 mA/V/cm, which means 667 mA produces 1 V/cm. E_{brain} is a whole brain E-field metric as the location of seizure duration is unknown.

The relationship from amplitude titration to hippocampal neuroplasticity is illustrated here (**Figure 4**). First, we demonstrate that amplitude-titrated seizure threshold increases with I/E_{brain} in non-human primates (**4A**). Second, we demonstrate that increased I/E_{brain} is related to decreased hippocampal E-field (current dependent metric, input current set here at 1 mA) (**4B1**). For fixed amplitude ECT, I/E_{brain} is inversely related to hippocampal volume change. E_{hippo} is the 95th percentile E-field in the hippocampus and will be an exploratory measure of this investigation. However, the focus on amplitude titrated seizure threshold requires E_{brain} , a whole brain E-field metric, as the regions involved in seizure induction are unknown. Third, we demonstrate that increased hippocampal E-field is related to increased hippocampal neuroplasticity across all amplitudes (600, 700, and 800 mA) and electrode placements (RUL and BT) (**4B2**). This relationship is a replication of the GEMRIC data (Figure 2) with our U01 data. Fourth, we performed an analysis of a subset of our data comparing I/E_{brain} with hippocampal volumetric change with 800 mA subjects (**4B3**).

Summary

[figure not shown]

Figure 4: The multi-step relationship from amplitude titration to hippocampal neuroplasticity.

A) Non-human primate data. $I_{\text{Electrode}}/E_{\text{brain}}$ (see description in Preliminary Data). Increased I/E_{brain} is related to increased amplitude required for seizure titration ($r = 0.84$, $p < 0.0001$).

B1) U01 data, all subjects. $I_{\text{Electrode}}/E_{\text{brain}}$ is inversely related to hippocampal E-field magnitude with an amplitude intensity of 1 mA, which is baseline for E-field modeling ($r = -0.79$, Cohen's $f^2 = 1.66$).

B2) U01 data, all subjects. Electrode placement (RUL and BT) and amplitude (600, 700, 800 mA) are based on the subject's last treatment. Right hippocampal E-field magnitude is directly related to right hippocampal neuroplasticity for all amplitude strengths (600, 700, and 800 mA) and electrode placements (right unilateral and bitemporal) ($r = 0.49$, Cohen's $f^2 = 0.33$).

B3) U01 data, subjects from the 800 mA arm. $I_{\text{Electrode}}/E_{\text{brain}}$ is inversely related to right hippocampal neuroplasticity for 800 mA subjects ($r = -0.62$, Cohen's $f^2 = 0.62$).

C1) Hypothesized relationship. Increased $I_{\text{Electrode}}/E_{\text{brain}}$ is related to increased amplitude required for seizure titration (verification of non-human primate data depicted in 4A).

C2) Hypothesized relationship (Go-No-go). The ratio of fixed amplitude ECT (800 mA) relative to amplitude seizure titration will be associated with right hippocampal neuroplasticity.

interpretation, and alternatives: To illustrate the application of these principles, we use our preliminary data (4B3) and hypothesized relationships (4C1 and 4C2). We also use the example of 2% hippocampal growth as optimal for antidepressant response (optimal hippocampal growth will be determined with a receiver operating curve

(ROC) curve predicting Inventory of Depressive Symptomatology (IDS-C30) total score decrease during the R61). With traditional 800 mA amplitude, the 2% volume increase is related to an I/E_{brain} of ~ 625 mA/V/cm (**4B3**) and fixed/amplitude ratio of ~ 2.7 (**4C2**). Subject #1 (orange star) has a low (250 mA) seizure threshold (ST) (**4C1**), I/E_{brain} of ~ 600 mA/V/cm (**4C2**) and a fixed/amplitude ratio of $800/250 = 3.2$ (**4C2**). Subject #1 will need an input current of $2.7 \times ST = 2.7 \times 250$ mA = 675 mA for 2% hippocampal volume increase. In contrast, Subject #2 (green star) has a high (350 mA) seizure threshold, I/E_{brain} of ~ 750 mA/V/cm and a fixed/amplitude ratio of $800/350 = 2.3$. In order to achieve the 2% volumetric increase, Subject #2 will require an increased X/amplitude ratio from 2.3 to 2.7. Subject #2 will need an input current of $2.7 \times ST = 2.7 \times 350$ mA = 950 mA for 2% hippocampal volume increase. We stress that the fixed/amplitude ratio ~ 2.7 for 2% hippocampal volume increase is conceptual and will be determined during the R61.

H1: Amplitude seizure titration will have a positive correlation with I/E_{brain} (**Figure 4C1**). This is a replication of the data from the non-human primate data. The relationship between I/E_{brain} and amplitude titration is the foundation for the rationale of this proposal.

Statistical approach for H1: Let $(x, y)_i$ be the observed vector of response for I/E_{brain} and seizure threshold for each patient, $I = 1, \dots, n$. The Pearson correlation will be calculated and the standard one-sided t-test with 2 degrees-of-freedom will be conducted for testing whether the correlation is positive, $H_0: \rho > 0$.

Power calculation for H1: The observed correlation in Figure 4A is $r = 0.84$ for non-human primates and we expect that the more conservative Cohen's "large" effect size $r = 0.5$ is a realistic lower bound for our population, thus a sample size of $n = 29$ provides 80% power at a $0.05 / 2 = 0.025$ significance level.

Go/No-Go criterion (H2): The ratio of amplitude titration to fixed amplitude ECT will demonstrate a linear relationship with treatment-responsive changes in hippocampal neuroplasticity. This relationship will determine the "neuroplasticity multiplier" to bridge from amplitude titration to hippocampal neuroplasticity.

Statistical approach for H2: We will perform a multiple regression accounting for covariates age and sex, $\%Vol_{Scaled} \text{ Change} = \beta_0 + \beta_1 M + \beta_2 \text{ age} + \beta_3 \text{ sex}$, where the effect size is $f^2 = R^2 / (1 - R^2)$, with R^2 the coefficient of determination with the interpretation of "the proportion of variance explained" in the response by the model over the grand mean. We will test whether the regression model explains a significant proportion of variance in the response, expecting that the key relationship is between $\%Vol_{Scaled}$ change and multiplier M .

Power calculation for H2: The relationship we are expecting in Figure 4C2 is derived from Figures 4B3 and 4C1. Starting with Figure 4B3, the relationship of I/E_{brain} on $\%Vol_{Scaled}$ change has a correlation of $r = -0.62$ with an effect size $f^2 = 0.624$, well above the Cohen's "large" effect size of $f^2 = 0.35$. Figure 4C1 is Figure A with the axes reversed, thus the correlation is $r = 0.84$. We will assume that the relationship between $\%Vol_{Scaled}$ Change and multiplier M will remain consistent with Cohen's "large" effect size. Then a sample size of $n = 36$ provides 80% power at a 0.05 significance level.

The Holm Procedure, a multi-step step-down procedure useful for endpoints with any degree of correlation, will adjust the two hypotheses below for multiple comparison³⁷. For our situation, this means H1 is tested at the 0.05 / 2 significance level and H2 is tested at $0.05 / (2-1) = 0.05$; however, H2 is tested only if H1 is significant.

The Go/No-Go criterion is set to "Go" if we can reject the null hypothesis that $H_0: \beta_1=0$ at a 0.05 significance level in the model specified in Hypothesis H2, that is, that multiplier M remains a significant predictor of $\%Vol_{Scaled}$ Change after adjusting for age and sex.

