## **6. Study Timelines**

Our total sample size (n = 40) allows for a conservative 20% attrition rate leaving a final sample size of 32. This recruitment rate of 20 subjects per year will complete subject recruitment 2 years after study initiation. We have a successful recruitment and retention history for ECT-imaging investigations of approximately 20 subjects per year with this demographic for the last decade and are well poised to meet the recruitment/enrollment goals delineated in this project proposal.

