Summary, interpretation, and alternatives: To illustrate the application of these principles, we use our preliminary data (**4B3**) and hypothesized relationships (**4C1** and **4C2**). We also use the example of 2% hippocampal growth as optimal for antidepressant response (optimal hippocampal growth will be determined with a receiver operating curve (ROC) curve predicting Inventory of Depressive Symptomatology (IDS-C30) total score decrease during the R61). With traditional 800 mA amplitude, the 2% volume increase is related to an  $I/E_{brain}$  of  $\sim 625$  mA/V/cm (**4B3**) and fixed/amplitude ratio of  $\sim 2.7$  (**4C2**). Subject #1 (orange star) has a low (250 mA) seizure threshold (ST) (**4C1**),  $I/E_{brain}$  of  $\sim 600$  mA/V/cm (**4C2**) and a fixed/amplitude ratio of  $800/250 = 3.2$  (**4C2**). Subject #1 will need an input current of  $2.7 \times ST = 2.7 \times 250$  mA = 675 mA for 2% hippocampal volume increase. In contrast, Subject #2 (green star) has a high (350 mA) seizure threshold,  $I/E_{brain}$  of  $\sim 750$  mA/V/cm and a fixed/amplitude ratio of  $800/350 = 2.3$ . In order to achieve the 2% volumetric increase, Subject #2 will require an increased X/amplitude ratio from 2.3 to 2.7. Subject #2 will need an input current of  $2.7 \times ST = 2.7 \times 350$  mA = 950 mA for 2% hippocampal volume increase. We stress that the fixed/amplitude ratio  $\sim 2.7$  for 2% hippocampal volume increase is conceptual and will be determined during the R61.

H1: Amplitude seizure titration will have a positive correlation with  $I/E_{brain}$  (**Figure 4C1**). This is a replication of the data from the non-human primate data. The relationship between  $I/E_{brain}$  and amplitude titration is the foundation for the rationale of this proposal.

Statistical approach for H1: Let  $(x, y)_i$  be the observed vector of response for  $I/E_{brain}$  and seizure threshold for each patient,  $I = 1, \dots, n$ . The Pearson correlation will be calculated and the standard one-sided t-test with 2 degrees-of-freedom will be conducted for testing whether the correlation is positive,  $H_0: \rho > 0$ .

Power calculation for H1: The observed correlation in Figure 4A is  $r = 0.84$  for non-human primates and we expect that the more conservative Cohen's "large" effect size  $r = 0.5$  is a realistic lower bound for our population, thus a sample size of  $n = 29$  provides 80% power at a  $0.05 / 2 = 0.025$  significance level.

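### The H1 test is written with 2 degrees of freedom instead of n − 2, and with the research hypothesis (ρ > 0) in place of the null

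*SAP*

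**What the plan says.** H1 in the SAP (section 1, Data Analysis) is directional: "Amplitude seizure titration will have a positive correlation with" I/E_brain. The data are one pair per patient, I/E_brain and "seizure threshold for each patient". A Pearson correlation is computed, and "the standard one-sided t-test with 2 degrees-of-freedom will be conducted for testing whether the correlation is positive". The same sentence then states the null: "testing whether the correlation is positive, $H_0: \rho > 0".

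Protocol section 13 (statistical approach for H1) has the same wording: "one-sided t-test with 2 degrees-of-freedom will be conducted for testing whether the correlation is positive", followed by the same null. Neither document gives n − 2 degrees of freedom, or a null of ρ ≤ 0 or ρ = 0, for H1.

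Three other statements bear on the point:

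- The H1 power paragraph, in both documents, plans 29 patients for 80% power at r = 0.5 and a significance level of 0.025.
- Protocol section 6 allows for 20% attrition from 40 recruits, "leaving a final sample size of 32".
- The multiplicity paragraph makes H2 conditional on H1: "however, H2 is tested only if H1 is significant".

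**The concern.** The sentence has two separate errors.

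**Degrees of freedom.** The t statistic for a Pearson correlation on n independent pairs has n − 2 degrees of freedom. Two would be right only for n = 4.

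**Null hypothesis.** The inequality labelled H0 is the claim the study hopes to support. There is no looser local meaning of H0 to explain this, because for H2 the documents use it conventionally: H0 is β1 = 0, and rejecting it gives the Go.

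This is the only sentence that defines the H1 test, and the H1 result decides whether the Go/No-Go test of H2 is carried out. If it stays as it is, someone must choose after the data are in between following the plan and correcting it. The two documents share the wording, so neither can be used to correct the other.

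**Working it through.** **Inputs.** Planning correlation 0.5, described as follows: "effect size $r = 0.5$ is a realistic lower bound for our population" (SAP, power calculation for H1). One-sided significance level 0.025 and n = 29 (same paragraph, with the one-sided test from the statistical approach). Final n = 32 (protocol section 6). Power figures use the exact distribution of r and assume bivariate normal data.

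**Step 1: reproduce the plan's n.**

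- Fisher z: n = ((z_0.975 + z_0.80) / atanh(0.5))² + 3 = ((1.960 + 0.842) / 0.5493)² + 3, which is 29.01 with unrounded quantiles.
- Exact power with n − 2 degrees of freedom is 79.9% at n = 28 and 81.4% at n = 29.

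The stated n = 29 is therefore the sample size of the ordinary one-sided test for a positive correlation.

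**Step 2: apply the degrees of freedom as written.** Take the usual statistic t = r√(n − 2)/√(1 − r²), keep rejection in the positive direction, and change only the reference distribution. The critical correlation is r_crit = t_crit/√(t_crit² + n − 2).

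| | n − 2 df | 2 df |
|---|---|---|
| Critical t, n = 32 | 2.042 | 4.303 |
| Critical r, n = 32 | 2.042/√(2.042² + 30) = 0.349 | 4.303/√(4.303² + 30) = 0.618 |
| Power at ρ = 0.5, n = 32 | about 85% | about 19% |
| Critical r, n = 29 | 0.367 | 0.638 |
| Power at ρ = 0.5, n = 29 | about 81% | about 16% |
| True one-sided type I error, n = 32 | 0.025 | 0.00008 |

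With the t(2) cutoff, 80% power is first reached at n = 84. A simulation of 200,000 draws at n = 32 gave 85.2% and 18.7%.

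**Step 3: one possible result.** Suppose r = 0.5 is observed at n = 32. Then t = 0.5 × √(30/0.75) = 3.162. The upper-tail p-value is 0.0018 with 30 degrees of freedom and 0.044 with 2. The first passes 0.025 and the second does not. Any observed r between 0.349 and 0.618 gives the same conflict, and the planning value lies in that band.

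**Step 4: apply the null as written.** If ρ > 0 is the null, rejection lies in the lower tail and is evidence against H1. With 30 degrees of freedom, n = 32 and ρ = 0.5, its probability is about 0.000001. The r = 0.5 result of step 3 would have a lower-tail p-value of 0.998.

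**The case against.** The best defence is that nobody would run the test this way. The sentence calls the test standard and one-sided and says it asks whether the correlation is positive. H1 is stated directionally, and n = 29 reproduces only if the ordinary test was meant. Degrees of freedom follow from n and are not an analyst's choice, and software will use n − 2. On this view the point is an erratum.

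The literal reading also has no single size. The figures in step 2 assume the usual statistic with only the cutoff taken from t(2). If 2 also replaced n − 2 inside the statistic, the critical r would be 4.303/√(4.303² + 2) = 0.95 and power would be practically zero. A null of ρ = 0 against ρ > 0 is as acceptable as ρ ≤ 0 and gives the same test. Finally, a lost 'n −' in the text extraction cannot be fully excluded.

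Most of this stands. The intent is clear, and the figures illustrate a literal reading; they do not forecast the analysis. It does not remove the point. The sentence as written contradicts the plan's own power statement, and it sits at the step that decides whether H2 is tested. The extraction argument is weak: the wording is the same in both documents, though their analysis sections largely duplicate each other. Even a lost 'n −' would leave the reversed null.

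**Conclusion.** The concern holds. Both errors are in the text of both documents and nothing elsewhere corrects them. They are most likely drafting slips, so the H1 sample size is not in question: with n − 2 degrees of freedom, n = 29 gives the stated 80% power and n = 32 gives about 85%.

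Taken literally, the degrees-of-freedom error would cut power at n = 32 to about 19%, and the reversed null would turn the test against H1. These sizes rest on ρ = 0.5, one-sided 0.025, bivariate normality and, for the 19%, the usual statistic with a t(2) cutoff in the positive direction. The point should be fixed before analysis. It is a certain error with an obvious intended meaning, but it lies in the test that H2 depends on.

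**What to change.** Replace the sentence in SAP section 1 and in protocol section 13 (statistical approach for H1) with wording to this effect: the Pearson correlation will be tested by a one-sided t-test with n − 2 degrees of freedom, of H0: ρ ≤ 0 against the alternative ρ > 0, where n is the number of patients with both measurements. A null of ρ = 0 would serve equally well.

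The cost is one sentence in each document. Sample size, alpha and study conduct are unaffected.

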## **29. Inclusion of Vulnerable Populations**

Sample inclusion will not include gender restrictions. It is expected that our sample will reflect the gender distribution of our ECT service over the last 5 years. Recruitment will reflect the demographics of the state of New Mexico. Prisoners will be excluded from the study. The age range of 50 to 80 years was selected because to limit the variability of age-related volume changes. Subjects with pre-existing diagnoses of neurodegenerative diseases or cerebrovascular pathology will be excluded. However, some older subjects may have significant cognitive deficits prior to treatment related to their depressive episode ("pseudo-dementia"). These subjects may not have decisional capacity for this investigation but are representative of a community sample receiving ECT in this age range. [name] (PI) and [name] (Co-PI) will assess decisional capacity of all subjects participating in this investigation. Subjects that do not have decisional capacity for this investigation will be able to participate in this research if they can assent to the procedure and a legally authorized representative (court appointed mental health treatment guardian) consents to the research protocol.

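### Two different tests are attached to H2: the stated approach and the n = 36 power figure use the whole-model F test, while the Go/No-Go rule tests β1 = 0

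*SAP*

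**What the plan says.** The SAP (section 1, Data Analysis) and Protocol section 13 carry the same text.

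- **Hypothesis.** H2 is labelled the Go/No-Go criterion. It says that the ratio of titrated to fixed amplitude is linearly related to hippocampal change.
- **Model.** "We will perform a multiple regression accounting for covariates age and sex": percent volume change is regressed on M (coefficient β1), age (β2) and sex (β3).
- **Test in the H2 approach paragraph.** "We will test whether the regression model explains a significant proportion of variance in the response". The effect size is f² = R²/(1 − R²), where R² is the variance explained "in the response by the model over the grand mean". The plan adds only an expectation that M is the main contributor.
- **Power.** The relationship with M is assumed to be one that "will remain consistent with Cohen's 'large' effect size", which the plan puts at f² = 0.35. On that basis n = 36 "provides 80% power at a 0.05 significance level".
- **Multiplicity.** H1 is tested at 0.025. H2 is tested at 0.05, and only after H1 succeeds. No test statistic is named for H2.
- **Decision rule.** The result is Go if β1 = 0 is rejected at 0.05, so that "multiplier M remains a significant predictor of" volume change after adjustment for age and sex.

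**The concern.** The null that matches H2 is β1 = 0. The null of the whole-model test is β1 = β2 = β3 = 0, so it is rejected if age or sex predicts volume change and M does not. An analyst following the H2 approach paragraph and one following the decision rule could report opposite H2 results from the same fitted model, and each could cite the plan.

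H2 is the scientific claim on which the neuroplasticity multiplier rests. A significant whole-model test driven by age could be reported as evidence of a ratio-to-neuroplasticity relationship beside a No-Go. Conversely, a Go could stand beside a non-significant H2. Either pairing invites a choice of test after the data are seen.

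**Working it through.** **Inputs.** From the documents: three predictors (M, age, sex); f² = 0.35, so R² = 0.35/1.35 = 0.259; α = 0.05; n = 36 for H2; 40 recruited with 20% attrition, leaving 32 (Protocol section 6). Assumed, because the documents give no value: the share of variance explained by age.

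**Formula.** Power = P(F′ > critical F), where F′ is noncentral F with u numerator df, n − 4 denominator df and noncentrality λ = n·f². The whole-model test has u = 3. The β1 test has u = 1, with f² read as the partial effect of M.

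**Step 1: reproduce n = 36.** For the whole-model test at n = 36, λ = 36 × 0.35 = 12.6 with 3 and 32 df, and power is 0.81. This is the smallest n that reaches 80%, so the stated figure matches exactly. The β1 test would need only n = 25 (λ = 25 × 0.35 = 8.75; power 0.805). The plan was therefore sized for the whole-model test, and the sentence in the approach paragraph is not merely loose wording.

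**Step 2: the whole-model test when M has no effect.** Set β1 = 0 and let age explain a share R² of the variance. For example, R² = 0.10 gives f² = 0.10/0.90 = 0.111 and λ = 32 × 0.111 = 3.56 at n = 32.

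| Assumed age R² | n = 32 | n = 36 |
|---|---|---|
| 0.05 | 15% | 17% |
| 0.10 | 28% | 32% |
| 0.15 | 43% | 49% |
| 0.20 | 59% | 65% |

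A simulation (20,000 trials, M independent of age and sex) at R² = 0.10 and n = 32 agrees. The whole-model test rejects in 28% and the β1 test in 5%. In 24% the whole-model test is significant and β1 is not; the decision rule would give No-Go in those trials.

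**Step 3: the reverse case.** Let only M matter, with R² = 0.26 and n = 32. In simulation β1 is significant in 84% and the whole-model test in about 71% of trials. In about 14%, β1 gives a Go while the whole-model test is not significant. The noncentral F gives higher values for the two tests (0.90 and 0.75). The simulated values are lower because the predictors vary from trial to trial.

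**Step 4: the H1 gate.** These rates apply to trials that reach H2. At the plan's r = 0.5 and n = 32, H1 passes in about 85% of simulated trials. If passing H1 is unrelated to the age effect, 28% becomes 0.85 × 28% ≈ 24% of all trials.

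**The case against.** The strongest reply is that the decision is already safe. H2 carries the label of the Go/No-Go criterion, and that criterion has an explicit rule: reject β1 = 0 at 0.05 with age and sex in the model. A reader might infer from the approach paragraph that an age effect could produce a false Go. The documents do not support that, because the β1 test keeps its 5% error rate whatever age and sex do. This part of the objection stands in full.

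A second reply is that the two tests form a sequence: an overall check, then a requirement that M remains significant. If both were required, the error for M would be below 5%. From the simulation at n = 32, both reject in 0.279 − 0.241 = 3.7% of trials at age R² = 0.10, and in 0.566 − 0.521 = 4.5% at 0.20. The reading is reasonable, but neither document states it.

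A third reply is that no family-wise failure has been shown. That is right. A reader might infer that the 5% family-wise level is broken, but this follows only if the whole-model test is the one meant in the Holm step. The text leaves that open.

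Finally, the age effect is hypothetical. Protocol section 29 says the age range was chosen "to limit the variability of age-related volume changes". That shows age was considered a source of variation, but also that the design tries to reduce it. It does not show that age predicts volume change over an ECT series. The percentages in the table are therefore illustrations.

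**Conclusion.** The inconsistency is real and worth correcting, though it does not undermine the Go decision. A hypothesis about M alone has been given, and powered for, a test that age or sex can reject, while the decision rests on a different test that has the right null. If the whole-model test is taken as the H2 result, the chance of reporting H2 as significant with no M effect is 15% to 59% at n = 32. This rests on an assumed age R² of 0.05 to 0.20 and applies to trials that have passed H1. In the other direction, about 14% of trials would give a Go with a non-significant whole-model test, if only M matters at R² = 0.26.

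Nor does the point show that the sample is too small for the Go test. If f² = 0.35 is the partial effect of M, the β1 test has about 0.90 power at n = 32. If 0.35 describes the whole model and is shared with age and sex, power for β1 is lower by an amount the documents do not allow one to compute.

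**What to change.** Make these changes in both the SAP and Protocol section 13:

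1. State that H2 is tested by the t-test (equivalently the partial F test with 1 and n − 4 df) of β1 = 0 in the age- and sex-adjusted model.
2. State that this is the Go/No-Go test and the test that receives 0.05 in the multiple-testing procedure.
3. Report the whole-model R² and F as descriptive only.
4. Restate the H2 effect size as the partial f² for M and redo the power statement. With partial f² = 0.35, 80% power needs n = 25, and power is about 0.90 at n = 32 and 0.93 at n = 36. Without this step, the f² definition and n = 36 would describe a test no longer used.

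The cost is a short text change in two documents and one revised power statement, with no new data and no additional model. The downside is that a significant whole-model F can no longer be cited as support for H2.
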